3 STUDY DESIGN

Prospective observational study of hospitalised and non-hospitalised patients post- infection with SARS-CoV-2. The study aims to recruit 2000 individuals, with proven COVID-19, who were not hospitalised but presented to Long-COVID clinics with persistent respiratory symptoms such as breathlessness or cough and are referred for cross-sectional imaging (computer tomography, CT) at baseline (3 months weeks after their first COVID-19 symptoms). The study will run for 18 months.

3.1 Study procedures objectives and outcomes

	Objectives	Outcome Measures	Timepoint(s)
Primary	1) Examine and compare the prevalence of ILD in patients with varying severity of COVID-19. (Non-hospitalised will be compared with hospitalised patients and COVID severity defined as varying levels of respiratory support)	MDT diagnosis of ILD at 12 months (+/- 3 months) after acute infection	12 months (+/- 3 months) post SARS-CoV-2 NB: Need 2 time points, 6 months apart, between 3 and 15 months post-acute SARS-CoV-2
Secondary	Determine progressive lung function impairment between 3 and 12 months	Lung function decline: ≥10% relative decline in FVC or DLco OR Imaging deterioration: increasing radiological extent of PC-ILD using image analysis or MDT discussion	Need 2 time points, 6 months apart, between 3 and 15 months post-acute SARS-CoV-2
	Resolution of ILD	Any of the following: ≥10% relative improvement in FVC, DLco, or reduction of radiological extent.	12 months (+/- 3 months) post SARS-CoV-2 Need 2 time points, 6 months apart, between 3 and 15 months post-acute SARS-CoV-2
	Persistence of ILD in those not meeting definition of progression or resolution		12 months (+/- 3 months) post SARS-CoV-2 2 time points, 6 months apart, between 3 and 15 months post-acute SARS-CoV-2
	Persistence of ILAs		12 months (+/- 3 months) post SARS-CoV-2

			Need 2 time points, 6 months apart, between 3 and 15 months post-acute SARS-CoV-2
	In hospitalised patients only: Assess the relationship between initial severity of acute infection and ILD	Markers of severity of acute infection (e.g. CRP)	12 months (+/- 3 months) post SARS-CoV-2 Need 2 time points, 6 months apart, between 3 and 15 months post-acute SARS-CoV-2
	In hospitalised patients only Assess the impact of specific medical therapy used in the acute setting and ILD e.g. antivirals, immunomodulation	Medical therapy used for acute infection	12 months (+/- 3 months) post SARS-CoV-2 Need 2 time points, 6 months apart, between 3 and 15 months post-acute SARS-CoV-2
	Evaluate breathlessness, fatigue and cognition	Medical research council dyspnoea scale Dyspnoea 12 FACIT-F Montreal Cognition Assessment (MOCA)	3 month, 6 months (+/- 6 weeks) and 12 months (+/- 3 months) post SARS-CoV-2 infection
	Evaluate the quality of life of patients with COVID-19	Short Form-36 (SF-36) EQ5D-5L	3 month, 6 months (+/- 6 weeks) and 12 months (+/- 3 months) post SARS-CoV-2 infection
	Assess impact of COVID19 on aerobic capacity and endurance.	Incremental shuttle walk test or cardiopulmonary exercise test, if clinically indicated	3 month, 6 months (+/- 6 weeks) and 12 months (+/- 3 months) post SARS-CoV-2 infection
Exploratory	Exploratory circulating biomarkers will be correlated with ILA/ILD	whole blood RNA sequencing (including peripheral blood mononuclear cells) and analysis of epigenetic modifications and proteomics	3 month, 6 months (+/- 6 weeks) and 12 months (+/- 3 months) post SARS-CoV-2 infection
	Compare serological and cellular measures of epithelial and endothelial injury and thrombosis	Serum biomarkers of epithelial and endothelial injury, NETosis and thrombosis Cellular measurements in these same patients. Serum/ Plasma: Nordic biomarkers, LRG-1, MMP-7 etc; NETs	3 month, 6 months (+/- 6 weeks) and 12 months (+/- 3 months) post SARS-CoV-2 infection
	Compare genetic risk factors for lung fibrosis and radiological progression, continuously and dichotomised	genome-wide array genotyping Genetic testing from blood/ saliva of putative candidate genes and use of GENOMIC data, and telomere length in a subset	No sooner than 3 month visit
	Assess the relationship between routinely collected laboratory parameters markers	Laboratory parameters (including CRP, FBC) and extent of ILD in patients	3 month, 6 months (+/- 6 weeks) and 12 months (+/- 3 months) post SARS-CoV-2 infection

3.2 Description of study procedure(s) Tier 1 and Tier 2

Initial patient approach

Eligibility assessment by clinical team

Study information and invitation letter provided to eligible patients for data only, Tier 1 participation.

Description of study procedure(s) Tier 2

History and Examination (10 mins) : Medical history, allergies, medications and anthropometric measurements including height, weight, and body mass index will be recorded during the study visit (or taken from the hospital notes. Or PHOPS data)

Blood sample collection (10 mins) :

Samples will be taken for plasma/ serum for epithelial and endothelial damage biomarkers, coagulation and genetics

Questionnaires (45 mins)

Participants will be provided with seven questionnaires; 36 Short-Form Survey (SF-36), Clinical Frailty Scale (CFS), Patient Health Questionnaire 9 (PHQ9), Montreal Cognition Assessment (MOCA), Dyspnoea-12 score, EQ5D-5L, FACIT-F at the end of each study visit.

There are no investigations required for participants co-enrolled in the PHOSP-COVID study.

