1.2 Study Rationale

Given the large number of patients infected with SARS-CoV-2, it is vital that the extent of PC-ILD is determined; its natural history defined particularly whether it is time-limited inflammation and reversible, or develops into persistent, or even progressive, fibrosis. Determining the natural history of PC-ILD, and risk factors as well as biomarkers related to outcome such as disease progression, will enable a precise approach to treatments such as immunomodulation or antifibrotic therapy [6], stratification into clinical trials, prognostication and appropriate service provision. This will facilitate assessment and prioritisation of both conventional and novel therapies used in the treatment of COVID-19 during the acute phase to mitigate the subsequent development of PC-ILD. By exploring the long-term implications of SARS-CoV-2 infection across the full spectrum of COVID-19 disease ranging from non-hospitalised patients managed in the community with mild symptoms to those requiring mechanical ventilation, we will define the risk factors for PC-ILD including disease severity, host genetic factors and the effects of antiviral and immunomodulatory treatment administered during the acute phase of the illness. The UKILD Post COVID study is a prospective multicentre observational cohort study that will be managed through the Imperial College National Heart and Lung Institute and funded by the UKRI Medical Research Council and an NIHR professorship ([name]).

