2.3 The primary endpoint

1. The primary endpoint of the study is as radiologically confirmed diagnosis of fibrotic or non-fibrotic ILD in the 12 months following COVID-19. Sub-studies will have a co-primary endpoint of change in the radiological extent of PC-ILD.

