3.3 Monitoring of clinical events and re-analysis of previous scans (clinically indicated)

Clinical outcome data and images from clinical scans for all COVID-19 patients will also be collected from around the time of infection and hospitalisation and follow up. Laboratory analyses and chest imaging results undertaken for clinical reasons will also be collected. Access to participant medical records and any relevant hospital data that is recorded as part of routine standard of care; i.e., CT-Scans, blood results and disease progression data etc. will be obtained with patient consent from hospital electronic patient records and NHS digital

3.4 Sample Handling Tier 2

Blood samples for the analysis of serum inflammatory markers, serum biomarkers of endothelial and epithelial injury and coagulation studies, viral serology, viral PCR, and whole genome sequencing, ribonucleic acid sequencing and flow cytometry in blood will be collected. Analysis of venous blood samples will be performed in local NHS laboratories. If the Participant consents approximately 10 ml of blood will be stored in the Division of Cardiovascular Medicine for further analysis as part of collaborations with other groups. Samples will not be collected from participants who are also participating in PHOSP-COVID

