6.4 Serious AEs

An SAE form should be completed and emailed to the Chief Investigator within 24 hours. However, relapse and death due to COVID -19, and hospitalisations for elective treatment of a pre-existing condition do not need reporting as SAEs.

All SAEs should be reported to the London Riverside REC where in the opinion of the Chief Investigator, the event was:

- 'related', ie resulted from the administration of any of the research procedures; and
- 'unexpected', ie an event that is not listed in the protocol as an expected occurrence

Reports of related and unexpected SAEs should be submitted within 15 days of the Chief Investigator becoming aware of the event, using the NRES SAE form for non-IMP studies. The Chief Investigator must also notify the Sponsor of all related and unexpected SAEs.

Local investigators should report any SAEs as required by their Local Research Ethics Committee, Sponsor and/or Research & Development Office.

Contact details for reporting [contact]**CI email (and contact details below)****Fax: N/A, attention [name]****Please send SAE forms to: [contact]****[contact] (Mon to Fri 09.00 – 17.00)****7.0 STATISTICS AND DATA ANALYSIS**

The prevalence of MDT-confirmed PC-ILD at both early (up to 6 months) and again at late (10-15 month) time-points and will be assessed within the total study population. The prevalence of broader radiological abnormalities and phenotypic patterns will also be assessed in a descriptive analysis, together with demographics, haematological and biochemical profiles, physiological performance, and patient-reported outcome measures. Analyses will be performed overall and stratified according to hospitalised and non-hospitalised, as well as severity of infection in hospitalised patients defined above.

Baseline and longitudinal changes in biomarkers reflecting PC-ILD evolution, including circulating factors and cell-types from detailed serological and cellular analysis, will be assessed in multilevel models for repeated measures to test associations according to the presence or absence of PC-ILD at late time points (10-15 months), and according to progression, resolution, or persistence of radiological patterns over follow up time points.

Analyses will be performed using standard epidemiological and statistical genetics methodology. This will include cross-sectional and longitudinal studies, and analyses of disease prevalence and incidence.

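### Late ILD status can be read anywhere in a 5 to 6 month window and is compared across severity groups with no term for time since infection, so elapsed time could enter the severity contrast.

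*Combined protocol and SAP*

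**What the plan says.** Three sections time the primary outcome differently.

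- Section 2.3 (primary endpoint): "radiologically confirmed diagnosis of fibrotic or non-fibrotic ILD in the 12 months following COVID-19".
- Section 3.1 (primary row): "MDT diagnosis of ILD at 12 months (+/- 3 months) after acute infection", with the added condition "NB: Need 2 time points, 6 months apart, between 3 and 15 months post-acute SARS-CoV-2". The objective in that row is to "Examine and compare the prevalence of ILD in patients with varying severity of COVID-19".
- Section 7.0: prevalence is assessed early, up to 6 months, and "again at late (10-15 month) time-points and will be assessed within the total study population".

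For the comparison itself, section 7.0 states: "Analyses will be performed overall and stratified according to hospitalised and non-hospitalised, as well as severity of infection in hospitalised patients defined above". It names no covariate for time since infection, no rule for choosing among several scans in the window, and no narrower-window sensitivity analysis. Its multilevel repeated-measures models concern biomarkers, with late PC-ILD status as one of the groupings. They do not cover the primary prevalence contrast.

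On scan dates, section 3.2.1 makes Visit 3 (about 12 months) obligatory, but the assessments it repeats from Visit 1 do not include CT. Section 3.3 adds: "Laboratory analyses and chest imaging results undertaken for clinical reasons will also be collected". Section 1.2 brings hospitalised participants in through PHOSP and non-hospitalised participants through Long-COVID clinics. In section 4.2, Tier 2 requires confirmed infection 3 months (+/- 6 weeks) earlier, while Tier 1 accepts infection at any time in the pandemic.

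**The concern.** Section 1.2 leaves the course of the disease open: "whether it is time-limited inflammation and reversible, or develops into persistent, or even progressive, fibrosis". The primary endpoint counts fibrotic and non-fibrotic ILD together, and both resolution and progression are secondary endpoints. A study set up to measure change should not take for granted that prevalence is flat across a window of 5 or 6 months.

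The main severity contrast, hospitalised against non-hospitalised, largely coincides with recruitment route. If one route tends to yield earlier late scans than the other, a simple stratified comparison cannot separate severity from elapsed time. The error could go either way. With falling prevalence, reading the more severe group earlier would exaggerate the contrast, and reading it later would dilute it. Even with equal timing, the 12-month prevalence is loosely defined while two late windows are in force and a participant with several late scans has no rule for which one counts.

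**Working it through.** The documents give no power calculation, alpha or target effect, so there is no design figure to reproduce.

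**Windows.** Section 3.1: 12 - 3 = 9 and 12 + 3 = 15, so 6 months wide. The two-reading condition does not narrow this: the earliest second reading is at 3 + 6 = 9 months and the latest at 15. Section 7.0: 15 - 10 = 5 months wide, with midpoint 12.5.

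**Illustration.** Suppose there is no true severity effect and both groups follow one prevalence curve but are read at different mean times.

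Inputs:
- Prevalence at month 12, p12 = 24%. This borrows the figure in section 1.1 for fibrotic changes on initial CT, given there as an upper value. Its use at month 12 is an assumption.
- Relative fall from month 9 to month 15, r = 10 to 30%: assumed.
- Gap in mean assessment time, g = 1 to 3 months: assumed.
- Two-sided alpha 0.05: assumed.
- Group sizes: 10,000 hospitalised and 2,000 non-hospitalised (section 1.2), plus smaller assumed sizes.

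Formulas:
- Linear curve: p(t) = p12 × [1 - s(t - 12)].
- p(15)/p(9) = 1 - r gives s = r / [3(2 - r)].
- With group means at 12 ± g/2, the spurious difference is D = p12 × s × g.

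Results:
- r = 10%, g = 1: s = 0.10/5.7 = 0.0175; D = 0.24 × 0.0175 × 1 = 0.4 points.
- r = 20%, g = 2: s = 0.20/5.4 = 0.0370; D = 0.24 × 0.0370 × 2 = 1.8 points (24.9% against 23.1%, odds ratio 1.10).
- r = 30%, g = 3: s = 0.30/5.1 = 0.0588; D = 0.24 × 0.0588 × 3 = 4.2 points (26.1% against 21.9%, odds ratio 1.26).

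The false rejection rate is Φ[(D - 1.96·SE0)/SE1] + Φ[(-D - 1.96·SE0)/SE1], where SE0 is the pooled and SE1 the unpooled standard error. For the central case at 500 against 500, SE0 = sqrt(0.24 × 0.76 × 2/500) = 0.0270 and SE1 is the same to four decimals. The rate is Φ(-1.30) + Φ(-2.62) = 0.097 + 0.004 = 10%.

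| Fall, gap | D (points) | 500 v 500 | 1,000 v 1,000 | 2,000 v 10,000 |
|---|---|---|---|---|
| None, or gap 0 | 0 | 5% | 5% | 5% |
| 10%, 1 month | 0.4 | 5.3% | 5.6% | 7.0% |
| 20%, 2 months | 1.8 | 10.1% | 15.4% | 40.5% |
| 30%, 3 months | 4.2 | 34.8% | 60.2% | 98.2% |

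At 10% prevalence, the 20% fall with a 2-month gap gives 0.7 points and 18% at 2,000 against 10,000.

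The last column is an upper end: 10,000 and 2,000 are recruitment or baseline figures, and fewer people will have a late scan. The bias in points does not depend on group size. The 3-month gap is also demanding. One group spread evenly over months 9 to 12 and the other over 12 to 15 have means of 10.5 and 13.5, a gap of 3. The same split of months 10 to 15 gives 11.25 and 13.75, a gap of 2.5.

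**The case against.** Bias needs both a timing gap and a drift in prevalence within the late window, and the documents show neither. Section 1.1 says that fibrotic changes do not appear to regress, so only the non-fibrotic part may move. Having resolution and progression as endpoints shows that change from the early reading is of interest, not that prevalence drifts between months 9 and 15. This objection stands, and it is why the size can only be illustrated.

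A reader might go further and infer that nothing aligns the groups in time. The documents do not support that. The groups share one window, Tier 2 entry is anchored at 3 months (+/- 6 weeks), and Visit 3 near month 12 is obligatory. Because Visit 3 lists no CT, these anchors constrain the scan date without fixing it. Nor does it follow that scans of PHOSP co-enrolees are untimed. Section 3.2 says only that this study requires no investigations of them, and PHOSP's own protocol is not among the documents. A 6-month gap would put every member of each group at opposite ends of section 3.1's window, and it is impossible under section 7.0's 10 to 15 months.

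It is also fair to say that section 7.0 names no covariates at all for this contrast, so time is not the only omission. Time differs, however, in that it is part of the endpoint's own definition.

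**Conclusion.** The point holds as a weakness in the planned analysis, not as a demonstrated bias. The late status is read over 5 or 6 months, section 2.3 gives a third timing, and the severity comparison has no adjustment for elapsed time. Equal timing is not ensured.

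Under the assumptions above, the spurious difference is about 0.4 to 4.2 points. In the central case it is 1.8 points, with false rejection of about 10% at 500 against 500 and about 40% at the recruitment figures. If timing is balanced or prevalence is flat across the window, the bias is zero. A reader might take the upper figures as the expected error; the documents contain no data on timing or drift that would justify this. The change is still worth making because it is cheap and also settles what the 12-month prevalence means.

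**What to change.** 1. Reconcile the windows in sections 2.3, 3.1 and 7.0.
2. Define one time origin, for example first symptoms or first positive PCR, with a rule for participants confirmed by serology only, since a positive serology result need not date the infection.
3. Use one late classification per participant, based on the scan nearest month 12 within the window, with the MDT decision tied to that scan.
4. Estimate late prevalence and the severity contrast from a model, such as a logistic model, that includes months from the origin to that scan (linear or spline). Standardise both to month 12 and check for a time-by-severity interaction.
5. Report the distribution of assessment time by severity group and add a narrower-window sensitivity analysis.

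If the time trend is correctly specified, false rejection in the scenarios above returns to about 5%.

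The cost is plan wording and modest analysis work, with no new visits or scans. Scan dates should be available: DICOM Study Date is not among the tags removed under the image management protocol (Appendix 1, Anonymisation details), and unlisted tags are retained. Some participants will have an uncertain infection date. The time term does not remove bias from scans whose timing depends on how ill the patient is, and the plan should state this as a limitation.

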2.4 The secondary endpoints

- 1) progressive lung function impairment between 3 and 12 months, defined as $\geq 10\%$ relative decline in FVC, or $\geq 10\%$ relative decline in DLco, or increasing radiological extent of PC-ILD using image analysis [20].
- 2) Resolution of ILD, as defined by $\geq 10\%$ relative improvement in FVC, DLco, or reduction of radiological extent.

- 3) Persistence of ILD in those not meeting definition of progression or resolution
- 4) Presence of interstitial lung abnormalities (ILA) on radiological images that do not meet definition of ILD.
- 5) A comprehensive series of clinical, molecular, MRI and biochemical parameters will be assessed as biomarkers.

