3.2.1 Baseline and follow up assessments

Initial patient approach

Eligibility assessment by clinical team

Study information and invitation letter provided to eligible patients

Visit 1 (~3 months) (Post COVID-19 infection patients)

1. Review of eligibility with participant
2. Obtain written informed consent
3. History and anthropometric measurements, e.g. height, weight, body mass index (BMI)
4. Blood sample (6-10 ml) collection
5. Pulmonary function test (20 minutes)
6. *Optional* 6-minute walk test (6MWT) (10 minutes)
7. Quality of Life questionnaire (SF-36) (10 minutes)
8. Clinical Frailty Scale (CFS) (5 minutes)
9. Personal health questionnaire (PHQ) (10 minutes)
10. Montreal Cognitive Assessment MOCA (10 minutes)
11. Dyspnea 12 score (10 minutes)
12. EQ5D-5L (10 minutes)
13. FACIT-F questionnaire (10 minutes)

Optional Visit 2 (~6 months) (Post COVID-19 infection patients and matched controls)

All visit 1 assessments will be repeated.

Visit 3 (~12 months) (Post COVID-19 infection patients)

All visit 1 assessments will be repeated.

Visits will be scheduled to take place over 1 day.

Visit 2 is optional,

Visits 1 and 3 are obligatory.

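### A fixed 10% change in FVC or DLco defines progression and resolution, but the plan does not fix the interval between tests, so spacing alone can change the class

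*Combined protocol and SAP*

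**What the plan says.** **The threshold.** Section 2.4 introduces the first secondary endpoint as "progressive lung function impairment between 3 and 12 months, defined as" a relative fall of at least 10% in FVC or DLco, or a growing radiological extent. Section 3.1 repeats the lung function criterion: "Lung function decline: ≥10% relative decline in FVC or DLco". Resolution is "Any of the following: ≥10% relative improvement in FVC, DLco, or reduction of radiological extent". The third class is the remainder: "Persistence of ILD in those not meeting definition of progression or resolution". None of these thresholds is expressed per unit of time.

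**The imaging route.** This is separate and carries no percentage: "Imaging deterioration: increasing radiological extent of PC-ILD using image analysis or MDT discussion".

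**The timing.** Four statements bear on it:

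- The progression objective in Section 3.1 is "Determine progressive lung function impairment between 3 and 12 months", a nominal 9 months.
- The timepoint column for progression and resolution says "Need 2 time points, 6 months apart, between 3 and 15 months post-acute SARS-CoV-2". It does not say whether 6 months is a minimum or an exact spacing, and it gives no tolerance.
- Section 3.2.1 places Visit 1 at about 3 months, an optional Visit 2 at about 6 and Visit 3 at about 12, and states that "Visits 1 and 3 are obligatory". Where Section 3.1 gives a 12-month timepoint, it allows 3 months either side.
- Section 7.0 uses other periods for prevalence: early, up to 6 months, and late, 10 to 15 months.

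No section says which pair of tests is used when Visit 2 was also attended. Section 7.0 describes multilevel models for biomarkers in which progression, resolution and persistence of radiological patterns enter as groups already formed. It does not adjust any class for the interval between tests.

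**The concern.** A fixed percentage is a sound definition of change only if everyone is observed over the same interval. Over a longer interval, a slower change reaches the threshold. Where lung function is still recovering after infection, the time of the first test matters too, because an early first test captures more of the recovery.

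Section 7.0 stratifies its analyses by hospitalised and non-hospitalised status, and the routes into the study differ:

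- PHOSP participants who are co-enrolled need no investigations within this study (Section 3.2).
- Data-only participants may have been infected at any point in the pandemic (Section 4.2), and their results come from clinical records.
- Tier 2 participants follow Visits 1 to 3.

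The documents set no common test schedule across these routes. If spacing or time of first test differs between the groups being compared, progression, resolution and persistence can differ between them without any difference in the course of disease.

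**Working it through.** The plan states no expected progression rate, sample size or power for these endpoints, so there is no figure of its own to reproduce.

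**1. Which intervals are possible?**

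- First test at month 3, late test at month 9 to 15: 9 − 3 = 6 months up to 15 − 3 = 12 months.
- Two tests within months 3 to 15 and at least 6 months apart: also 6 to 12 months.
- With the Tier 2 entry window of 3 months ± 6 weeks (about 1.5 to 4.5 months), the visit windows alone would allow 9 − 4.5 = 4.5 up to 15 − 1.5 = 13.5 months.
- With the Section 7.0 periods and a first test no sooner than month 3: 10 − 6 = 4 up to 15 − 3 = 12 months.

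The rest of the check uses 6 to 12 months, the range on which the first two readings agree.

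**2. What steady rate reaches the threshold?** Linear rate = 10% / interval. Compound decline = 1 − 0.9^(1/interval).

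| Interval (months) | Linear, % per month | Compound decline, % per month |
|---|---|---|
| 6 | 10/6 = 1.67 | 1.74 |
| 9 | 10/9 = 1.11 | 1.16 |
| 12 | 10/12 = 0.83 | 0.87 |

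Rates from 0.83% up to, but not including, 1.67% per month fall short at 6 months and count at 12. A decline of 1.25% per month is 7.5% at 6 months (not progression on that measure), 11.25% at 9 and 15% at 12 (progression at both). Rates outside this band get the same class at 6 and 12 months. Resolution mirrors this, and persistence takes whatever the other two leave.

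**3. How large could the effect be?** The documents give no slopes, measurement error or distribution of intervals, so everything in this step is assumed. With T the interval in months, individual slopes normal with mean m and SD s (% per month), and error SD e (percentage points) on the change:

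- P(decline of at least 10%) = Φ[(−10 − mT)/√((sT)² + e²)], with m = −0.3, s = 0.6
- P(gain of at least 10%) = 1 − Φ[(10 − mT)/√((sT)² + e²)], with m = +0.5, s = 0.8

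For example, progression at T = 6 with e = 5: (−10 + 1.8)/√(12.96 + 25) = −8.2/6.16 = −1.33, so P = 0.092.

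Results for e = 5, one lung function measure:

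| Interval (months) | Progression | Resolution |
|---|---|---|
| 6 | 9.2% | 15.6% |
| 8 | 13.6% | 23.0% |
| 9 | 16.1% | 26.5% |
| 10 | 18.5% | 29.8% |
| 12 | 23.3% | 35.6% |

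- Everyone at 12 versus everyone at 6 months: ratio 2.5 for progression, 2.3 for resolution.
- Everyone at 10 versus everyone at 8 months: 1.36 and 1.30.
- Everyone at 9.5 versus everyone at 8.5 months: 1.16 and 1.14.

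The 12-versus-6 ratio depends heavily on e. For e = 3, 5 and 7 it is 5.1, 2.5 and 1.8 for progression, and 3.2, 2.3 and 1.8 for resolution. The direction is the same in each case.

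**The case against.** **The spacing may be meant as exactly 6 months.** A fixed spacing would remove most of the problem, and the text does not rule it out. But the obligatory pair, about 9 months apart, would then fail the rule, and so would the stated period of months 3 to 12. A minimum of 6 months is the more coherent reading, but it is an inference. On either reading the passages need reconciling.

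**The large ratios are extremes.** A reader might infer that progression rates will more than double through timing. The documents do not support that. The 2.3 to 2.5-fold figures place whole groups at opposite ends of the range, while the scheduled visits centre on 9 months.

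**Straight lines are assumed.** If recovery slows or levels off, the length of the interval matters less and the time of the first test matters more. This limits the resolution figures in particular.

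**The 10% rule is only part of the endpoint.** Imaging change alone can classify a participant. If an independent imaging route classified 20% whatever the interval (an assumption), progression would be 1 − 0.8 × (1 − 0.092) = 27.3% at 6 months and 1 − 0.8 × (1 − 0.233) = 38.6% at 12, a ratio of 1.41. Imaging change may also depend on the interval, but not through a 10% threshold.

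**Intervals may not differ by group.** A reader might infer that they will. The PHOSP test schedule is not in the documents, so only the possibility can be stated. The comparison of hospitalised with non-hospitalised people in the primary objective concerns ILD diagnosis and does not use the 10% rule.

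**Time-based modelling is not excluded.** Section 2.4 counts clinical parameters among the biomarkers, and Section 7.0 promises longitudinal studies. Neither commits to modelling FVC or DLco on time.

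These points reduce the likely size and the certainty of harm. They do not remove the dependence of class on spacing.

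**Conclusion.** The concern holds for the FVC and DLco components of the secondary endpoints. The threshold is unscaled, the timing statements conflict, and the windows allow intervals of about 6 to 12 months. The twofold range in the rate needed, 1.67% against 0.83% per month, follows from the plan's own figures under steady change.

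The effect on reported proportions cannot be calculated from the documents. About 1.3 to 1.4-fold for 8 versus 10 months illustrates a moderate imbalance, with 2.3 to 2.5-fold at the extremes. Both rest on assumed linear slopes, an error SD of 5 percentage points and a single measure. Bias between groups arises only if spacing or time of first test differs between them, which the plan neither prevents nor adjusts for. The primary endpoint is unaffected. This should be corrected before analysis, but it does not threaten the main result.

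**What to change.** 1. Reconcile the timing text in Sections 2.4, 3.1, 3.2.1 and 7.0. State whether 6 months is a minimum, what tolerance applies, and which pair of tests is used when Visit 2 exists, for example the pair closest to months 3 and 12.
2. Analyse FVC and DLco as continuous measures in a mixed model on actual time since infection. Report the group-level change from month 3 to month 12 alongside the 10% classes.
3. Adjust every comparison of the 10% classes for interval length and time of first test. Add a sensitivity analysis restricted to intervals near 9 months.
4. Do not derive individual month 3 to 12 classes by extrapolating from two tests. Visit 2 is optional, so many participants may have only two tests, and extrapolation would lean on the linearity that is in doubt.

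The cost is some added analysis text and one model per measure, with no new visits. Infection and test dates must be captured for every route, including data-only and PHOSP participants; the documents do not state that test dates are recorded. The model-based change is slightly harder to explain than a raw percentage.
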